4.4.4 Package and labeling of the study products

Tested product and comparator product will be prepared and provided by Sponsor. Sponsor will provide clinical centers with the test product and comparator product.

Study product Uritos[®] is manufactured by Kyorin Pharmaceutical Co. Ltd (Japan). Sponsor of the study (R-Pharm JSC), according to licensing agreement with manufacturer of the study product Kyorin Pharmaceutical Co Ltd (Japan), possesses the rights development, authorization and commercial promotion of the drug product Uritos[®].

Within the frames of the study Sponsor is responsible for provision of package, labeling, shipping of the study products dedicated for the clinical study in accordance with shelf life and expiration date.

4.4.4.1 Study product

Dosage form: Film-coated tablets; 0,1 mg.

Package:

Uritos[®] for this clinical study will be provided in bottles, each bottle containing 200 tablets.

Labeling:

Study products labeling will conform to the local regulations and requirements. Study product will be labeled in Russian language with designation of the following information: Uritos[®], film-coated tablets, Manufacturer, Storage conditions, Batch No; Expiration date; Patient No; For clinical trials; Study No; Center No, Patient No, Sponsor of the study.

4.4.4.2 Comparator product

Dosage form: Film-coated tablets; 2 mg.

Package:

Urotol for this clinical study will be provided in blister pack with 14 tablets per pack made of PVC/PVDC/AI. 2 or 4 blisters per carton pack together with package insert.

Labeling:

Study products labeling will conform to the local regulations and requirements. Study product will be labeled in Russian language with designation of the following information: Urotol, film-coated tablets, Manufacturer, Storage conditions, Batch No; Expiration date; Patient No; For clinical trials; Study No; Center No, Patient No, Sponsor of the study.

4.5 Duration of patients' participation in the study, description of visits order and duration of all study periods, including follow-up period visit

The study provides:

- Screening period – up to 2 weeks (14 days)
- Treatment period – therapy is performed during 12 weeks (84 days), including randomization visit (Day 1), 3 treatment phase visits on Weeks 2, 4 and 8 and end of the study visit on Week 12 (Day 85). Permissible variation during treatment visits ± 3 days.
- Follow-up period visit – 30 (+5) days after the end of study treatment, finishes with follow-up period visit and end of participation of the patient in the study (Days 114 - 119).

Maximum observation period of the patients within the study is 136 days (screening not exceeding 14 days + therapy up to 84 days (± 3 days) + observation period up to 35 days.

4.5.1 Beginning of the study

- Beginning of the study is considered to be opening visit in the first research center. In Russian Federation, according to the Federal law “On Medicine Circulation”, head of medical institution within terms, not exceeding 3 business days from the start of clinical study of the medicinal product for medical use informs about this authorized federal authority of the executive branch of the government, approved performance of this study, according to the established form (part 3.1 was introduced by the Federal law of 29.11.2010 No 313-Ф3).
- Before the start of any procedures and actions connected with the study, patients should be provided with comprehensive and reliable information concerning any aspects of the preformed study. Each potential participant of the study should be informed of its objectives, methods, anticipated benefits and risks/ inconveniences associated with the study. All information concerning study course, benefits and possible risks is presented in Patient information list with form of informed consent, dated and signed by patient in two copies. One copy is provided to the participant of the study (see Section 12.4).
- Before the start of participation in the study all patients are discussed with and being warned about necessity to use reliable birth control methods during whole study period and, within at least 30 days, after the end of study (see Section 4.5.3.1).
- Before the start of participation in the study patient should be informed that he/she will receive qualified medical health as appropriate, as well as that information of the patient derived during study, will be confidential, that is stated in Patient’s information list.
- According to Article 5.3 of Order No 266 of Ministry of Health of the Russian Federation, Investigator and/or healthcare institution are obliged to inform patient concerning requirement of treatment of the diseases, revealed during the course of the clinical study. This information should be recorded in the source documents and Sponsor should be informed about these cases (newly discovered disease within the clinical study is classified as adverse event).
- Each research center will be keeping record of the List of identification codes of the patients with full patient name, initials, date of birth, identification code, assigned during screening, status (unsuccessful screening, finished the study, prematurely withdrawn from the study). This list is stored in the center and is not subject to transfer to sponsor.
- Moreover, Patients screening and inclusion log will be filled where data of informed consent signing, screening visit date, identification code, assigned during screening, initials, failed screening (yes/no), randomization date and randomization number will be included.

4.5.2 Determination of the end of study

Finishing of the study for the patient is considered to be the last examination/procedure, performed during follow-up visit for safety parameters assessment.

4.5.3 Study visits and assessments

Screening procedures will be undertaken following signing of Informed consent form.

Graphical scheme of the scheduled procedures for each visit are presented in the Table 5.

4.5.3.1 Visit 1 (Screening): Days from -14 to -1

Screening period should not exceed 14 days before randomization visit/beginning of therapy.

During the screening patient’s conformity towards inclusion/non-inclusion criteria is verified.

During screening visit following receipt of informed consent from the patient acquisition of baseline information of the patient, including demographic data (sex, date of birth, race, body mass, height), medical anamnesis, diagnosis, concomitant pathology and previous and concomitant therapy with designated date of start of product administration and doses within 30

days before screening visit; for female and male patients – birth control methods, for female patients – terms of menopause beginning.

Patient fills out OAB Awareness Tool Questionnaire for assessment of overactive bladder symptoms severity.

Physical examination with BP and HR assessment is performed.

Assessment and registration of adverse events starts from the moment of signing of informed consent form.

Clinical and biochemical blood tests (ALT, AST, bilirubin, creatinine, total protein, glucose, alkaline phosphatase, cholesterol, potassium, sodium) and urinalysis will be performed in the central laboratory. Serological examination for HIV, hepatitis B and hepatitis C is performed. Moreover, PSA testing is performed in male patients.

US-examination of kidneys, bladder and urine excretory ways with residual urine volume assessment is performed for exclusion of bladder structural pathology.

Cough probe is performed for assessment of urethral sphincter capability in women.

12-lead ECG is performed.

Female patients of childbearing potential undertake pregnancy test using dipstick (in the research center).

- All patients should be discussed with efficient birth control issues:

Female patients of childbearing potential and male patients and their female partners should use at least two birth control methods, one of those is barrier, including double barrier contraception method (condom in combination with intravaginal spermicide, cervical caps with spermicide, diaphragms with spermicide) during the whole study period and at least 30 days following administration of the last dose of the study product. Moreover, in addition to barrier contraception method, female patients of childbearing potential may use other approved birth control method:

- Oral, transdermal, implantational and injectional hormonal therapy;
- Intrauterine device (IUD).
- Partner's vasectomy (if patient was exposed to vasectomy, nevertheless barrier contraception method should be applied).

Female patients of childbearing potential before the start of the study should be informed about importance of birth control measures during the study, potential risk factors associated with pregnancy occurrence and, moreover, that in case of pregnancy occurrence they should immediately inform investigator physician. Female patients, not having menstruations for 2 years and more before inclusion into the study, as well as female patients subjected to surgical intervention (surgical sterilization, bilateral ovariectomy, hysterectomy etc) are considered as female patients without childbearing potential. These patients may be free from requirements concerning contraception described above.

Male patients, participating in the study, should be also informed, that in case of pregnancy appearance in their female partners they have to notify Investigator physician about this circumstances.

Patient is issued the diary where he/she should make notes concerning number of urination episodes, number of incontinence episodes at daytime (from 7 am to 11 pm) and nighttime (from 11 pm to 7 am), number of awakenings, number of micturition urgency episodes, as well as administration/missing doses of the study product and adverse events.

Investigator explains to the patients rules for diary filling, schedules next visit date and requests for daily filling of diary and reminds to take the diary to the next visit.

4.5.3.2 Visit 2 (Randomization/Beginning of the therapy): Day 1

During the Visit 2 patient's conformity towards inclusion/non-inclusion criteria is repeatedly verified by Investigator. Patient, conforming to the inclusion criteria and not possessing non-inclusion criteria, randomly assigned into correspondent therapy group by randomization procedure (according to Section 4.3.1).

Randomization day and day of start of therapy are designated to be Day 1 and is considered to be baseline point for calculation of following visits schedule.

Prior to randomization:

Patient fills out OAB Awareness Tool Questionnaire and Quality of life Questionnaire EQ-5D.

Check up of diary filling results is performed.

Assessment of concomitant therapy, physical examination with BP and HR assessment, adverse events assessment and registration is performed.

Female patients of childbearing potential undertake pregnancy test using dipstick (in the research center).

US examination of the bladder with residual urine volume assessment is performed.

If patients is recognized to be fully conforming to inclusion/non-inclusion criteria, randomization procedure is performed with following assignment into treatment group (according to Section 4.3.1).

Following randomization:

Investigator provides patient with comparator product according to randomization result in amount, sufficient for administration before the next visit, and explains how to take the product and reminds to return all packs from the product at the following visit.

First administration of the study product is performed at the day of randomization.

Patient is issued diary for the following filling. Investigator explains to the patients rules for diary filling, schedules next visit date and requests for daily filling of diary and reminds to take the diary to the next visit.

4.5.3.3 Visits 3, 4, 5 (Treatment phase visits): Days 15 (± 3), 29 (± 3), 57 (± 3)

Visit 3 takes place after 2 weeks ± 3 days after beginning of therapy (Day 15 ± 3).

Patient fills out OAB Awareness Tool Questionnaire.

Assessment of concomitant therapy, physical examination with BP and HR assessment, adverse events assessment and registration is performed.

Investigator gathers packs of previously issued study product from the patient, performs calculation of returned product for assessment of compliance maintenance and gives next pack of the product for further intake.

Check up of diary filling results is performed; afterward diary is returned to the patient for further filling. Investigator explains to the patients rules for diary filling, schedules next visit date and requests for daily filling of diary and reminds to take the diary to the next visit.

Visit 4 takes place after 4 weeks ± 3 days after beginning of therapy (Day 29 ± 3).

Patient fills out OAB Awareness Tool Questionnaire. Assessment of concomitant therapy, physical examination with BP and HR assessment, adverse events assessment and registration is

performed.

US examination of the bladder with residual urine volume assessment is performed.

Investigator gathers packs of previously issued study product from the patient, performs calculation of returned product for assessment of compliance maintenance and gives next pack of the product for further intake.

Check up of diary filling results is performed; afterward diary is returned to the patient for further filling. Investigator explains to the patients rules for diary filling, schedules next visit date and requests for daily filling of diary and reminds to take the diary to the next visit.

Visit 5 takes place after 8 weeks \pm 3 days after beginning of therapy (Day 57 \pm 3).

Patient fills out OAB Awareness Tool Questionnaire. Assessment of concomitant therapy, physical examination with BP and HR assessment, adverse events assessment and registration is performed.

Clinical and biochemical blood tests (ALT, AST, bilirubin, creatinine, total protein, glucose, alkaline phosphatase, cholesterol, potassium, sodium) and urinalysis will be performed in the central laboratory.

US examination of the bladder with residual urine volume assessment is performed.

Investigator gathers packs of previously issued study product from the patient, performs calculation of returned product for assessment of compliance maintenance and gives a sufficient quantity of study drug for administration till the next visit. Partly used study drug packs are returned to the patient for further administration..

Check up of diary filling results is performed; afterward diary is returned to the patient for further filling. Investigator explains to the patients rules for diary filling, schedules next visit date and requests for daily filling of diary and reminds to take the diary to the next visit.

4.5.3.4 Visit 6 (End of treatment) Day 85 (\pm 3)

Visit 6 takes place after 12 weeks \pm 3 days after beginning of therapy – at the next day following intake of the last dose of the study product (Day 85 \pm 3).

Patient fills out OAB Awareness Tool Questionnaire and Quality of life Questionnaire EQ-5D.

Assessment of concomitant therapy, physical examination with BP and HR assessment, adverse events assessment and registration is performed.

Clinical and biochemical blood tests (ALT, AST, bilirubin, creatinine, total protein, glucose, alkaline phosphatase, cholesterol, potassium, sodium) and urinalysis will be performed in the central laboratory.

Female patients of childbearing potential undertake pregnancy test using dipstick (in the research center).

US examination of the bladder with residual urine volume assessment is performed.

12-lead ECG is performed.

Diaries are taken from the patients with the following check of diary filling results.

Investigator gathers packs of previously issued study product from the patient, performs calculation of returned product for assessment of compliance maintenance.

Decision is taken concerning further patient management.

4.5.3.5 Visit 7 (Follow-up examination visit): after 30 \pm 5 following end of treatment

Visit 7 should take place after 30 \pm 5 following end of treatment for assessment of safety of the

treatment performed (days 114 - 119). Visit can be performed through telephone connection without need for physician appointment by patient.

Assessment of concomitant therapy, physical examination with BP and HR assessment (are not performed in case of telephone contact), adverse events assessment and registration are performed.

4.5.3.6 Unplanned visit

If patient prematurely withdraws from the study at any stage, it is required, if possible, to perform all procedures associated to premature withdrawal from the study visit within one week following decision of patient withdrawal. Procedures of this visit are identical to the procedures of the end of treatment visit (Visit 6).

Table 5 Timetable of basic procedures of the study

	Visit 1	Visit 2	Visit 3 (2 weeks ± 3 days)	Visit 4 (4 weeks ± 3 days)	Visit 5 (8 weeks ± 3 days)	Visit 6 (12 weeks ± 3 days)	Visit 7 (30 + 5 days after end of treatment)
Days (D)	D from - 14	D1	D15 (±3)	D29 (±3)	D57 (±3)	D85 (±3)	D114 -
Reception of the informed consent	X						
Demographic data ¹ /patient history acquirement	X						
Previous and concomitant therapy assessment	X	X	X	X	X	X	X
Assessment and registration of AE	X	X	X	X	X	X	X
Physical examination ²	X	X	X	X	X	X	X ³
Complete blood count ⁴	X				X	X	
Blood chemistry ⁵	X				X	X	
Urinalysis ⁶	X				X	X	
Serological examination (HIV, Hep B and C)	X						
PSA level assessment (male only)	X						
Pregnancy test (only women with child-bearing potential)	X	X				X	

US-examination of kidneys, bladder and urine excretory ways (residual urine volume assessment)	X						
US examination of the bladder with residual urine volume assessment		X		X	X	X	
Cough probe	X						
12-lead ECG	X					X	
Assessment with OAB Awareness Tool Questionnaire	X	X	X	X	X	X	
Quality of Life assessment with EQ5D Questionnaire		X				X	
Issue/return and assessment of the diary	X	X	X	X	X	X	
Randomization		X					
Study product issue:		X	X	X	X		
Study product return, compliance assessment			X	X	X	X	

¹ Sex, date of birth, race, body mass, height

²Physical examination includes vital parameters assessment

³Is not conducted in case of telephone contact with the patient

⁴Hemoglobin, hematocrit, white blood cells and differential blood count, platelets.

⁵ ALT, AST, bilirubin, creatinine, total protein, glucose, alkaline phosphatase, cholesterol, potassium, sodium

⁶ Specific gravity, pH, protein, urinary sediment

4.5.4 End of the study

Clinical center should entirely finish the study and fill out all required documentation in accordance with protocol. The study may be suspended before its official finish in case of appearance of objective reasons, either by Sponsor, or by clinical center. Notifications concerning study cessation should be submitted to all parties, taking part in the study within the shortest possible time. Any extension of study terms should be coordinated between Sponsor and clinical center with corresponding documentation.

4.5.5 Description of several study procedures

4.5.5.1 Physical examination and vital parameters assessment

Full physical examination of all organs and systems will be performed at screening visit (Visit 1) and before randomization (Visit 2). During all following visits abbreviated physical examination is permitted with determination of significant deviations from baseline conditions (deviation-associated data are recorded as AE/SAE). Physical examination during every visit includes assessment of vital parameters (arterial pressure [BP], heart rate [HR]). BP and HR should be

assessed at resting state in sitting position.

4.5.5.2 Laboratory parameters

Following laboratory rests will be performed in central laboratory.

- **Complete blood count:** Hemoglobin, hematocrit, WBC and full blood count, platelets count – during screening, on Week 8 of treatment (Visit 5) and after the end of therapy (Week 12, Visit 6).
- **Blood serum biochemistry:** ALT, AST, bilirubin, creatinine, total protein, alkaline phosphatase, cholesterol, potassium, sodium – at screening on Week 8 (Visit 5) at the end of therapy (week 12, Visit 6). Before blood sampling for biochemical analysis patient should refrain from food and drink only water for, at least, 8 hours.
- **Urinalysis:** Specific gravity, pH, protein, urinary sediment – during screening, on Week 8 of treatment (Visit 5) and after the end of therapy (Week 12, Visit 6).
- **Serological testing for infections:** Blood analysis for presence of antibodies to HIV, antibodies to Hepatitis C virus, Hepatitis B virus (HBsAg) is performed during screening only.
- **Total prostatic specific antigen (PSA) level:** Assessment is performed in all male patients only during screening. Assessment result is used for validation of patient's conformity to inclusion/non-inclusion criteria (PSA exceeding 4 ng/ml is considered to be non-inclusion criteria).

Detailed description of laboratory probes acquirement, handling, storage and shipping, materials (tubes and labels) as well as normal values range of laboratory parameters will be provided in laboratory manual. Laboratory examinations results, performed in central laboratory, will be sent to Investigator by e-mail.

Investigator should validate results and assess remarks (notes) in laboratory tests prints. In case of deviations clinically significant changes should be emphasized. Investigator should sign and date the laboratory tests prints approving their verified status.

Following laboratory rests will be performed in the research center:

- Urine pregnancy test should be performed with use of dipsticks for female patients of childbearing potential – during screening visit, before randomization (Visit 2) and after finishing of the therapy (Visit 6). Test result has to be negative during screening visit and randomization visit for inclusion into study. For dipstick pregnancy test performance Sponsor of the study will be supplying centers with dipsticks for human chorionic gonadotropin (hCG) level evaluation in urea. Test results are fixed in the source documents. Dipsticks are not entitled to storage and should be discarded after results record following local practices.

4.5.5.3 US-examination of kidneys, bladder and urine excretory ways

US-examination of kidneys, bladder and urine excretory ways is performed according to local research center practice by functional diagnostics specialist during screening, uUS examination of the bladder with residual urine volume assessment is performed before randomization (Visit 2), at week 4 of treatment (Visit 4), at week 8 of treatment (Visit 5) at the end of therapy (week 12, Visit 6). Abdominal access is preferable. This examination is directed towards exclusion of organic pathology of urinary system before prescription of the study therapy and residual urine volume assessment (in ml) before the start of the study and during the study course. US-examination is performed on filled urinary bladder. Patient should not take diuretics the day before examination. Following measurement of full urinary bladder patient is asked to empty it and US-examination is performed second time for measurement of residual urine volume.

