4.3.2 Treatment blinding

This study is performed as open-label so that investigators and participating patients will be aware of the product administered to the patients.

4.4 Description of treatment method applied within the study, dosage and administration schedule of the study product. Description of pharmaceutical form, package and labeling of the study product

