8 SAFETY ASSESSMENT

8.1 List of safety parameters

- 1) Frequency for development of adverse events (AE) and serious adverse events (SAE).
- 2) Frequency of development of AE and SAE, depending on application of the product.
- 3) Frequency of development of AE and SAE, bringing to treatment cessation/withdrawal from the study.
- 4) Residual urine volume assessment using US-examination of the bladder at the study visits against study start visit.
- 5) Changes of laboratory parameters, ECG parameters and vital parameters assessment.

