9.9 Safety assessment

For longitudinal safety variables (laboratory analysis data) mean, standard deviation, median, minimum and maximum should be provided. For nominal variable group frequencies and percent of patient for each demographic category should be provided.

All AE should be presented as a list and coded in accordance to the MedDRA terminology of lower grade (version on data lock point). AE started before administration of the study product

should not be included into analysis.

Frequency of all AE should be summarized (number and percent of patients in which AE were reported at least once during the study) concerning interaction with the study product, assessed by investigator, and by severity grade.

For comparison of AE appearance in the study groups χ^2 test of exact Fisher test is planned to be applied, for comparison of manifestation rate Mann-Whitney U test will be applied.

Laboratory parameters (total blood count and blood biochemistry, urinalysis), vital parameters will be assessed separately to each group with the following comparison using paired Student t-test for connected samples (for parameters with normal distribution) or using non-parametric Wilcoxon signed rank test for connected samples (for parameters with ordinary scale type or in case of significant distribution deviations from normal).

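### Residual urine volume is a named safety criterion, but section 9.9 pre-specifies no between-arm estimate for it, and nothing addresses whether the on-treatment scan operator knows the arm

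*Combined protocol and SAP*

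**What the plan says.** **Criterion.** Section 8.1 (repeated in the synopsis, 1.3) lists as safety parameter 4: "Residual urine volume assessment using US-examination of the bladder at the study visits against study start visit".

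**Measurement.** Section 4.5.5.3 has the full ultrasound "performed according to local research center practice by functional diagnostics specialist during screening". The same sentence continues to the bladder scan at Visits 2, 4, 5 and 6 without naming an operator. Residual volume is recorded in ml. The section fixes some scan conditions: full bladder, no diuretics the day before, abdominal access preferred, and a second scan after voiding. It provides for no central reading.

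**Blinding.** Section 4.3.2 states that "investigators and participating patients will be aware of the product administered to the patients". It does not mention ultrasound staff.

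**Analysis.** Section 9.9 contains:
- descriptive statistics: "For longitudinal safety variables (laboratory analysis data) mean, standard deviation, median, minimum and maximum should be provided";
- a between-arm test for adverse events only: "For comparison of AE appearance in the study groups", by chi-square or Fisher, with Mann-Whitney for manifestation rate;
- tests for other safety data: "Laboratory parameters (total blood count and blood biochemistry, urinalysis), vital parameters will be assessed separately to each group", using a "paired Student t-test for connected samples (for parameters with normal distribution") or the Wilcoxon signed rank test.

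**Objective.** Section 2 aims to show a similar safety profile to the comparator. Section 3 asks for safety relative to tolterodine.

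**The concern.** A safety criterion measured in ml, with a pre-randomization baseline and three on-treatment scans, should lead to an estimate of the difference between arms. Here the route from criterion to analysis breaks off at 9.9. Reading residual volume into the laboratory paragraph would not repair this, because a paired test asks whether each arm changed from its own baseline. One arm's change can be significant and the other's not without the arms differing, and the reverse is also possible.

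Bladder emptying matters for this drug class. Section 2.3.1 lists urine retention among the clinically significant reactions and asks for close monitoring. If the between-arm analysis is chosen after the data are seen, in an open-label trial, the visit, model and summary are all open to choice.

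The secondary issue is who takes the reading. The trial is open to investigators and patients, and the plan is silent on the scan operator. If that person is not the investigator, keeping the arm from them is a cheap safeguard that the plan leaves out.

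**Working it through.** **1. Follow the criterion through the plan.**

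| Place | What it gives for residual volume |
|---|---|
| 1.3 and 8.1 | Named criterion, on-study visits against study start |
| 4.5.5.3 and Table 5 | Scans at Visit 2 (before randomization) and Visits 4, 5, 6 |
| 9.1 and 9.1.1 | General rule: analyzed values tabulated and plotted; registered characteristics summarized by treatment group |
| 9.3 | General rule: two-sided 95% confidence intervals for other data; no variable, model or visit named |
| 9.8 | Efficacy only |
| 9.9 | Not named; non-AE tests are paired within group; between-arm tests are for AEs |

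No section names a between-arm estimate, model, time point or population for criterion 4.

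**2. Reproduce the plan's sample size (9.2).** Inputs: SD 2.12, margin 0.8, one-sided alpha 0.025, power 80%, 1:1.

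n = 2 × 2.12² × (0.84 + 1.96)² / 0.8² = 110.1, rounded up to 111 per arm, 222 in total. This matches. (The fraction as printed shows 0.02 in the denominator; 111 follows from 0.8² = 0.64. This does not bear on the point.)

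**3. What a between-arm comparison of volume could detect.** The documents give no SD for residual volume, so results are in SD units. For a two-sided 5% comparison of means with 80% power and no credit for baseline adjustment:

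difference = (1.96 + 0.84) × √(2/n)
- n = 111 per arm: 2.80 × 0.1342 = 0.38 SD
- n = 150 per arm: 2.80 × 0.1155 = 0.32 SD

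**4. What the adverse-event comparison could detect.** Section 2.3.1 gives residual urine as a reaction in 8/435 = 1.84% in additional imidafenacin trials. No tolterodine rate is given. With 1.84% in one arm and an assumed higher rate in the other (two-sided 5%, normal approximation):

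| Assumed rate, other arm | Power, 111 per arm | Power, 150 per arm |
|---|---|---|
| 3.6% | 12% | 15% |
| 5.4% | 29% | 38% |
| 9.0% | 66% | 79% |

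On these assumptions the adverse-event route is a weak substitute for the measured volume.

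**5. Sensitivity to observer bias (assumed shifts, no true difference).** Chance that a nominal 5% test rejects, with z = shift / √(2/n):

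| Assumed shift in one arm | 111 per arm | 150 per arm |
|---|---|---|
| 0.1 SD | 12% | 14% |
| 0.2 SD | 32% | 41% |
| 0.3 SD | 61% | 74% |

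This shows only how sensitive such a test would be. It is not evidence that readings would shift.

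**The case against.** **The data are not ignored.** Sections 9.1 and 9.1.1 promise tables and graphs by treatment group, and 9.3 promises two-sided 95% intervals for other data. A residual volume judged clinically significant could also be recorded as an adverse event (8.3.1) and compared under 9.9. This stands. A reader might infer that residual volume goes unused or cannot be tested, and the documents do not support that. What they lack is a pre-specified between-arm estimate.

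**The operator's knowledge of the arm is not stated.** The specialist phrase belongs grammatically to the screening scan, when no arm has been assigned. That the same role performs the Visit 4, 5 and 6 scans is an inference from the sentence running on with nobody else named. A reader might infer that operators are told the product or that readings are biased; neither is in the documents. The scan conditions in 4.5.5.3 also remove some variation. This stands, and it makes masking the secondary part of the point.

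**The 1.8% has limited reach.** It is an imidafenacin rate for residual urine. A reader might carry it over to both arms, or conclude that retention will be too rare to compare. Section 2.3.1 gives retention frequency as unknown, and other urinary events such as dysuria are also collected, so volume is not the only bladder-safety information.

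**ANCOVA is one choice among several.** True, but it respects the criterion's definition: with Visit 2 volume as covariate, the treatment difference is the same whether the outcome is the value or the change from Visit 2. Section 9.8 already uses this model for efficacy.

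**Conclusion.** The point holds in this form: criterion 4 is named and measured, the safety objective is comparative, and no between-arm estimate is pre-specified for it. That conclusion comes from reading the plan and needs no assumption. ECG parameters, part of safety criterion 5, are likewise not named in 9.9.

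The primary endpoint and the sample size are unaffected. The loss is a comparison that the planned data could support at about 0.32 to 0.38 SD. That range assumes comparable means and between 150 and 111 patients scanned per arm; its value in ml cannot be given without an SD.

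The masking part is an inexpensive safeguard. It rests on the inference that someone other than the investigator performs the on-treatment scans. The size of any observer bias is unknown, and the documents do not show that bias would occur.

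**What to change.** **Main change, section 9.9.** Add: residual urine volume at Visits 4, 5 and 6 will be compared between arms in the safety population by ANCOVA, with Visit 2 volume as covariate and treatment as factor; the adjusted difference will be given with a two-sided 95% confidence interval, together with the number scanned per arm at each visit. Optionally, tabulate by arm the share at or above 100 mL, the figure used in non-inclusion criterion 3. This would be a descriptive reporting category only, with no role in patient management.

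**Secondary change, section 4.5.5.3.** Add: where a functional diagnostics specialist other than the investigator performs the Visit 4, 5 and 6 scans, that person is not told the study product and does not see the treatment record, and the patient is asked not to disclose it.

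**Cost.** A short paragraph and one or two table shells in the analysis, and one instruction at the sites. No added visits, scans or patients. Masking may sometimes fail because the patient knows the arm.
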